Participants will be recruited from the Maryland Psychiatric Research Center (MPRC) Healthy Control Pool (HP-00042350), MPRC screening protocol (HP-xxxxx) or by advertisements (approved by IRB prior to using). All persons who qualify for this study are referred to the recruiter (PI and/or PI staff) and then contacted and asked if they would like to participate in this study. Interested persons undergo a brief telephone screening followed by an in-person interview. After the initial telephone screen, all potential healthy controls undergo a SCID interview. We will use random digit dialing as our primary source for identifying healthy controls. For random digit dialing, we will utilize contact information lists purchased from Survey Sampling International (SSI), a leading provider of sampling, data collection and data analytic solutions for survey-based research. SSI compiles contact information lists based on census and market-based research data.

Participants with SRDs:

Potential participants with SRDs will be recruited from three sources: the Maryland Psychiatric Research Center (MPRC) clinical programs: the Outpatient Research Program (ORP), the Treatment Research Program (TRP), and the First Episode Clinic (FEC); local outpatient mental health centers; and a standing recruitment database, from which we have enrolled participants in previous MPRC clinical trials.

Potential MPRC and community participants will be identified primarily through chart review or nomination by their primary clinicians who are aware of study entry criteria and demands, and have been asked to identify clinically stable patients who may be interested in research

participation. MPRC and community participants may also be self- or peer-referred for this study.

Healthy controls will be matched to participants with SRDs by age, gender and parental SES level. The planned total enrollment is 50 participants with SRDs and 50 healthy controls, which, under the assumption of 10% attrition, will result in 45 completers in each group. We will enroll 18 participants per year. In each year, we will plan to recruit an equal number of participants with SRDs and healthy controls to avoid potential cohort effects.

Assessments: All of the following assessments will be conducted blind to treatment assignment.

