hemodynamic delay. The condition-specific responses will be assessed by performing regression analyses against these functions. Within condition responses, which reflect a condition minus baseline contrast, will be assessed for each of the conditions. Between-condition differences will be assessed by contrasting the task-specific responses with each other. A fixed effects analysis will be performed by entering whole run sequences for all the participants into a single analysis and regressing each sequence against all conditions. Random effects analysis will be used to assess differences between group fMRI data. For this analysis, the contrasts from the first level analysis for each individual will be used to represent mean response patterns for that individual, and between-condition or between-group analyses will be performed. Due to hypothesis regarding anterior cingulated/medial frontal, dorsolateral frontal and hippocampal involvement, between-group differences for BOLD activation within these regions will be examined with an ROI mask approach. In addition, the BOLD signal change will be extracted from these ROIs for each group to examine the hemodynamic time course. In order to obtain the functional connectivity characteristics, we will first manually draw the ROIs for each individual based on anatomic landmarks. Manually traced ROIs nicely overcome the issue of group structural differences. We will use these ROIs to extract the eigenvariates of time series in each participant. The second step will be to elucidate the functional connectivity of each ROIs with the whole brain by a seed-voxel analysis (extracting the weighted mean time series and then entered as covariates in a whole-brain regression analysis). The individual connectivity images created will be taken to a second-level analysis to obtain the connectivity characteristics of these 3 regions at the group level. The next step will be to determine if our a priori ROIs are correlated to each other by calculating the correlations between eigenvariates of each ROI. DMN: For resting state fMRI analysis we will use white matter time course as a regressor, assuming it will contain similar spurious fluctuations as in the gray matter. We will use SPM segmentation module to segment the whole brain white matter. The time course of white matter will be averaged. We will regress out the six head motion parameters and the average white matter time course before cross correlation analysis. Cross correlation maps are then converted to z score maps using an AFNI built-in function. Correlation analyses will be performed by calculating the correlation coefficient between each voxel's time course and the averaging time courses of all the voxels in the defined regions of interest. We will use ROI seed based analyses for all hypothesis testing. Manually traced ROIs overcome the issue of group structural differences. Independent component analysis (ICA), small-world network, SEM, and Granger causality methods can be used to analyze resting state fMRI data. These methods may extract additional circuit information. However, there are still challenges in these methods (113). We will use ICA primarily for extracting the default mode network component for additional exploratory analyses. The Granger causality and small-world brain network methods require some a priori definition of brain regions and the resultant topologic properties of brain networks are highly dependent on the number of brain regions, which remains to be fully evaluated for multiple group x drug comparisons (114,115). A seed-based method is preferred here for testing a priori hypotheses that address specific brain regions. It also takes advantage of this method's higher sensitivity and ease of interpretation (116). 4.4.3.2 MRS: Spectra will be analyzed using the fully automated, standard curve-fitting software, LCModel. Metabolites will be referenced to water and only metabolites of good fits (CRBs< 20) will be included. Voxels will be segmented into CSF, gray, and white matter tissue using SPM8 and in house Matlab code; metabolites will be corrected according to Gasparovic et al. (117). This method produces excellent reliability for glutamate and glutamine as determined by a test-retest reproducibility study in 10 healthy controls scanned twice separated by about 1 week. All spectra were of excellent quality (the average FWHM was 0.021 ppm and the average SNR was 44). Spectral quantification yielded excellent fits as illustrated with Cramer–Rao lower bounds (CRLB) less than 10 for Glu and Glu+Gln and 23 for Gln and test-retest coefficients of variation (CVs) of 9.3 for Gln and 4.2 for

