
Glu, absolute percent differences of 13.8 for Gln and 3.8 for Glu, and intra-class correlations (ICCs) of 0.82 for Gln and 0.89 for Glu.

Study Design:

Evaluation Phase: There will be an approximate 2-week Evaluation Phase, during which potential participants will undergo baseline assessments to determine whether they meet inclusion criteria. Participants will be clinically stable, with clinical stability defined as two consecutive CGI ratings with no change in score.

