Tryptophan Acquisition and Study Dosing: TRYP is a dietary supplement, whose use is regulated under the FDA Dietary Supplement Health and Education Act of 1994 (DSHEA). We will obtain TRYP powder from Ajinomoto, North American Inc and we have approval under an IND for use in this population. On the morning of the challenge studies, TRYP or placebo (lactose monohydrate) powder will be diluted in water (250 mL) into a slurry immediately prior to oral intake (119). The participant will be instructed to drink the full 250 mL over a one minute time period. The unblinded pharmacist, not participating in assessment procedures, will prepare and dispense the study medications.

Randomization and Blinding:

Treatment assignment (placebo and TRYP) will be randomly assigned, with each participant receiving each condition on separate occasions. Participants will be randomly assigned using a permuted block randomization system with separate randomization sequences for healthy

controls and schizophrenia patients. Treatment assignment order is random within each block, and an equal number of subjects are assigned to each treatment within a block. The block sizes will vary in random sequence and randomization will be matched by age and gender. Thus, it will be difficult to ascertain the next treatment assignment, even if a subject becomes unblinded, while the imbalance of numbers between the treatment groups is kept within tight limits. Randomization requests are sent to the study statistician, who sends a coded treatment assignment to an unblinded pharmacist. Separate emergency unblinding envelopes for each subject will be kept in a locked cabinet at each dispensing pharmacy. All raters, investigators and other staff will be blind to treatment assignment except for the pharmacist. The pharmacist does not participate in study assessments and conveys no information about treatment assignment to subjects or staff except in a medical emergency.

Payment:

Participants will be paid \$15 per hour for each visit (approximately 3 hours for Evaluation and approximately 7 hours for each Challenge visit) as well as \$100 for completion of each Challenge visit. The total payment for the study will be approximately \$455.

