Statistical Analysis: Initially, we will examine responses to TRYP or placebo challenge separately in healthy controls and participants with schizophrenia-related disorders (SRD), anticipating that different basal states of KYNA metabolism may result in distinct responses to TRYP challenge in the two groups. Secondary analyses will compare responses to TRYP challenge in the two groups.

Primary Aims:

- 1): To determine if TRYP-induced elevated KYNA levels impair performance on neuropsychological measures of attention, processing speed verbal and visual memory, and working memory.

Analysis plan: To facilitate comparison of the magnitude of effects across the six cognitive tests from the MCCB, we will utilize the MCCB T-scores for each test. For each cognitive measure, we will fit a mixed model for repeated measures ANCOVA: post-study drug score on i-th day = pre-study drug score on i-th day + treatment on i-th day + day + treatment x day, where day (=1,2) is an indicator of whether the scores were collected on the first or second day of testing. In this model, the treatment effect estimates the average TRYP - placebo difference across the two possible orders of testing, and the treatment x day effect estimates how much this difference might depend on whether TRYP or placebo was administered first. Learning effects from repeated cognitive testing could produce diminishing increases across the four repeated administrations of each test, resulting in larger pre-post differences in scores on the first versus second day of testing; these learning effects could be different following dosing with TRYP versus placebo, masking the existence of treatment x day interactions. Since the MCCB tests were chosen to have small learning effects ($d < 0.1$; 101), we anticipate these learning effects and possible interactions with treatment will be small. To take account of multiple testing with six cognitive tests, we will use the Benjamini-Hochberg False Discovery Rate (FDR; 120) modification of the Bonferroni method: we will compare the six p-values from largest to smallest to successively stricter critical values $c_j = 0.05 \times (6-j+1)/6$; if the j-th p-value is less than c_j , we will reject that null hypothesis and all null hypotheses corresponding to smaller p-values. To compare the magnitude of T-score differences between TRYP and placebo among cognitive tests, we will add terms for cognitive test and test x treatment interactions to the model described above.

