2): To determine if TRYP-induced elevated KYNA levels alter neural circuit activation and connectivity between the dorsolateral prefrontal cortex (DLPFC) and hippocampus (HPC) during the performance of the Relational and Item-Specific Encoding (RISE; 90) task.

Analysis Plan: In healthy controls and individuals with SRD, we will compare intensity of BOLD signal activation in DLPFC and hippocampus, using the mixed model for repeated measures ANOVA: BOLD activation = treatment + ROI + task condition (item encoding, relational encode, item/relational recall) + treatment x task condition + treatment x ROI + treatment x ROI x task condition + order of treatments + interactions with order, with analyses performed separately in each group. A similar model will be used to examine functional connectivity or correlations between fluctuations in BOLD signal activation between DLPFC and HPC in each task condition, using similar methods previously used to test nicotine challenge effect on resting state functional connectivity (121). To assist in meeting normality assumptions, Fisher's z transformation will be applied to correlation coefficients measuring task-related connectivity prior to modeling.

3): To determine if TRYP-induced elevated KYNA levels alter glutamate levels in the medial (mPFC), a brain region hypothesized to be important in the performance of cognitive tests.

Analysis plan: We will estimate the effect of TRYP or placebo on glutamate in healthy controls or SRD separately and compare whether it is different in these two groups by fitting the mixed model for repeated measures ANOVA: glutamate in mPFC = group + treatment + order + treatment x group + interactions with order, where group indicates healthy controls or individuals with SRD, treatment indicates receiving TRYP or placebo on a given day, and order indicates whether the active treatment is given on the first or second session. In the event of significant interactions between order and treatment, we will examine treatment effects for each order separately; otherwise, order effects will be dropped from the model.

Secondary Aims:

1): To examine if TRYP-induced elevated KYNA levels alter resting patterns of default network activation and connectivity.

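### Aim 3 splits the tryptophan effect by order when treatment x order is significant, but that term is the session contrast, so each split estimate confounds tryptophan with session

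*Combined protocol and SAP*

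**What the plan says.** The Aim 3 analysis plan fits a repeated-measures mixed model, "glutamate in mPFC = group + treatment + order + treatment x group + interactions with order", and defines the order term: "order indicates whether the active treatment is given on the first or second session". Order is thus the sequence a participant was randomised to, and the model has no term labelled session or day. The decision rule follows: "In the event of significant interactions between order and treatment, we will examine treatment effects for each order separately"; if the interaction is not significant, the order terms are removed.

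Three other places bear on this:

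- Under Study Design, the Double-Blind Challenge Phase has two visits, with TRYP at one and placebo at the other. Scanning takes place once per visit, after dosing, so there is no pre-dose glutamate value.
- Under Randomization and Blinding, the two orders are balanced: "an equal number of subjects are assigned to each treatment within a block".
- The Aim 1 analysis plan includes day in the model and says that "the treatment effect estimates the average TRYP - placebo difference across the two possible orders of testing". Aim 3 has no such statement.

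**The concern.** In a two-session, two-sequence crossover, a significant treatment x order term is what an ordinary change between visits produces. Measured glutamate may drift between visits for reasons unrelated to TRYP. Splitting by order does not remove that drift. It leaves the drift inside each order-specific TRYP-placebo difference, with opposite sign in the two orders.

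Aim 3 is a primary aim. Depending on how the split results are read, the rule could report visit drift as a TRYP effect, or lose a real TRYP effect because only one order shows it. The plan does not say which reading applies, and does not say that the average over orders is still to be reported after a split.

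**Working it through.** **1. Inputs**

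- Completers (Recruitment): 50 x (1 - 0.10) = 45 per group, which reproduces the plan's figure, "will result in 45 completers in each group". Balanced orders give 23/22 within a group and 45/45 over both groups.
- Glutamate variability (MRS part of Neuroimaging Processing and Analyses): "test-retest coefficients of variation (CVs) of 9.3 for Gln and 4.2 for" glutamate, i.e. 4.2%. Taken as the within-person SD, the SD of a TRYP-placebo difference is 4.2 x √2 = 5.94%.
- Sensitivity value (same section): "absolute percent differences of 13.8 for Gln and 3.8 for Glu". If 3.8% is a mean absolute difference and the data are normal, the SD of the difference is 3.8 x √(π/2) = 4.76%.
- Assumed, because the documents give no value: a session shift D of 0, 1, 2 or 3%; two-sided 0.05 for every test.

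**2. Algebra**

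Let τ be the TRYP effect and D the session 2 minus session 1 shift. With no carryover and the same τ in both sessions, the expected TRYP-placebo difference is:

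- TRYP first: τ - D
- Placebo first: τ + D
- TRYP first minus placebo first (treatment x order): -2D
- Average of the two orders: τ

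With carryover λT from TRYP and λP from placebo, the interaction becomes -2D - (λT + λP) and the average becomes τ + (λP - λT)/2. If the TRYP effect is τ1 in session 1 and τ2 in session 2, the interaction becomes -2D - (τ2 - τ1) and the average becomes (τ1 + τ2)/2. In each case the interaction mixes D with the other quantity and cannot separate them.

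**3. Aliasing check**

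On the 8 group x order x session cells with ±1 coding, treatment x order equals session up to sign, and treatment x order x group equals session x group up to sign. The Aim 3 model has 8 columns and rank 8. Adding session gives 9 columns and still rank 8. Replacing the two interactions by session and session x group gives 8 columns and rank 8.

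**4. Precision**

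Standard error of the average: 5.94 x √[(1/23 + 1/22)/4] = 0.89%. Within one order: 5.94/√23 = 1.24% and 5.94/√22 = 1.27%.

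**5. Simulation of the rule**

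There were 40,000 trials per scenario, with no carryover. Treatment x order was tested either within one diagnostic group or in the two-group model. If p < 0.05, a one-sample t-test was done within each order of one group; otherwise a pooled paired t-test was used. The true TRYP effect is 0, and significance in either order after a split counts as a finding.

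| Session shift | 0% | 1% | 2% | 3% |
|---|---|---|---|---|
| Rule, interaction tested in one group | 8% | 18% | 50% | 85% |
| Rule, interaction tested in both groups | 6% | 18% | 54% | 86% |
| Session-adjusted average | 5% | 5% | 5% | 5% |
| Order always dropped | 5.0% | 4.8% | 3.8% | 2.9% |
| Rule, SD of difference 4.76%, one group | 8% | 24% | 69% | 96% |
| Rule, SD of difference 4.76%, both groups | 6% | 25% | 72% | 97% |

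When the split is triggered with a true effect of 0 (SD of difference 5.94%), the two order-specific estimates have opposite signs in 97-99.6% of trials (one-group test) or 83-98% (two-group test).

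**6. The stricter reading**

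If both orders must be significant in the same direction, false findings stay at or below 5%. With τ = -2% and D = 2%, the order-specific expectations are -2 - 2 = -4% and -2 + 2 = 0%. Power is then 24% (one-group test) or 8% (two-group test), against 60% for the session-adjusted average.

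**The case against.** The strongest reply accepts the algebra and disputes the harm.

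- **The shift is not documented.** True. The 50-86% figures need an assumed 2-3% shift. With no shift the rule gives only 8% or 6% against 5%. The protocol reports good one-week reliability for glutamate (ICC 0.89), although ten controls cannot exclude a shift of this size. The smaller SD implied by the 3.8% figure makes the error rates larger.
- **The decision reading is not stated.** Also true. The plan does not say whether one order or both must be significant, so the false-positive and power figures are alternatives and do not add up. In the -2%/2% scenario the either-order reading keeps power at 82-87%. If the split is only a descriptive supplement to an overall estimate, neither harm occurs, but the plan does not say so.
- **The fitted model already contains the right average.** Correct while all order terms are kept: under effect coding its treatment contrast within a group is the session-adjusted average. The defect lies in the sentence that leads away from that estimate.
- **The rule guards against carryover or an order-dependent TRYP effect.** It cannot. The test does not distinguish these from drift, and the split estimates still contain the drift. It does stand that calling the interaction a pure session contrast requires a constant TRYP effect and no carryover.

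The branch that drops order when the interaction is not significant is not at fault. With balanced orders, dropping order does not inflate error.

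**Conclusion.** The concern holds, and the rule must be changed before analysis. That each split estimate confounds TRYP with session follows from the design and needs no assumed figure. There is no pre-dose scan that could remove a shift.

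The size is conditional. It rests on a session shift of 0-3%, which is assumed, on the protocol's own test-retest figures for variability, on 45 completers per group, and on no carryover. Under these, the either-order reading takes the false-finding rate from 6-8% with no shift to about 85% at a 3% shift. The both-orders reading protects that rate but can cut power from 60% to 24% or 8%. The order-averaged, session-adjusted estimate avoids both problems, provided carryover is not differential.

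**What to change.** In Aim 3:

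- Replace treatment x order with a session (1/2) fixed effect that is always retained, and replace treatment x order x group with session x group. Keep order as a nuisance main effect. Do not add session alongside treatment x order, because the two are aliased.
- Report one within-participant TRYP-placebo effect per diagnostic group, averaged over the two orders. State that it assumes no differential carryover and that, if the TRYP effect differs between sessions, it estimates the mean of the two.
- Delete the split-or-drop sentence. Show order-specific means descriptively only.

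Two wording changes elsewhere would keep the plan consistent. In Aim 2, which has no split rule, label the treatment x order term as session. In Aim 1, say that day carries the order-dependence of the within-person difference, and that treatment x day is the between-participant sequence contrast; the Aim 1 treatment estimate is unchanged.

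The cost is SAP wording only. No new data are needed, and the model uses one degree of freedom per group more than dropping order would.
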